1. To determine if the total number of hospitalizations related to respiratory event is lower in the interactive arms (Arm 2 and Arm 3) than in the control group (Arm 1).

Secondary Endpoints

1. To recognize, evaluate, and treat respiratory events through telecommunications with or without remote monitoring before the requirement of hospitalization or result of death.
2. To improve compliance in multiple areas noteworthy to IPF patients as measured by various means during clinic appointments to help guide further understanding and education:
 - a. IPF medication compliance – by patient report/diary
 - b. Laboratory follow up – by patient report and collection of laboratory reports
 - c. Attendance in pulmonary rehab or other formal exercise program – by patient report and/or collection of rehabilitation records
 - d. Supplemental oxygen use – by patient report
 - e. Management of comorbidities
 - i. GERD – by patient report of medication use and lifestyle changes
 - ii. OSA – by collection of compliance reports of pap therapy, or notes of such contained in office notes
 - f. Vaccines – by patient report
3. To improve quality of life scores as demonstrated by QOL questionnaires
4. To compare hospitalization parameters of “time to first hospitalization”, length of stay, number of hospitalizations per individual, and outcomes (such as quality of life post-hospitalization), discharge status [alive, deceased], discharged to [home, hospice facility].
5. To improve patient knowledge of lung disease, treatments, and management as demonstrated by self-report
6. To compare measurements obtained by clinic spirometry and home spirometry and clinic pulse oximetry and home oximetry.

Exploratory Endpoints

Exploratory endpoints will be collected to determine if the activities related to telehealth and remote monitoring will positively affect physiology and mortality.

1. To evaluate the difference in forced vital capacity (FVC) from baseline/diagnosis among the groups and as stratified by class
2. To evaluate the difference in walk distance in six minutes from baseline/diagnosis among the groups and as stratified by class

3. To compare findings in annual echocardiography in regards to right ventricular size and function and pulmonary hypertension from baseline/diagnosis among the groups and as stratified by class
4. To evaluate mortality differences among the groups and as stratified by class

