APPENDIX 6: TREATMENT COMPLIANCE QUESTIONNAIRE

The following questionnaire will be given to patients at Baseline, Month 3, Month 6, then every 6 months. This will be given as a survey via the RED Cap database, or as a paper-based product for the patient to complete and return. The purpose of this survey is to evaluate patient-reported compliance with IPF treatments and therapies, as well as evaluate the patient's general knowledge about his disease. Both sections of the questionnaire will be scored. The values of the answers for the Compliance Section are recorded in parenthesis below. The scoring of the Educational Section is as follows: Completely agree = 3 points, Mostly agree = 2 points, Somewhat agree = 1 points, Do not agree = 0 points. A higher score will reflect an overall greater compliance or knowledge level.

Compliance section

Do you take your IPF medication (nintedanib or pirfenidone) daily and as prescribed?

- A. Yes, I take my medication for IPF daily (3)
- B. Yes, I take my medication for IPF daily, but not always as prescribed. (3)
- C. No, I do not take my medication daily, but take it most days of the week. (2)
- D. No, I only take my medication less than half the days in a week. (1)
- E. No, I do not take my medication. (0)
- F. This is not applicable to me because I am not currently prescribed IPF medication. (n/a)

Do you get your safety labs completed for your IPF medication monthly or quarterly?

- A. Yes, I get my safety labs completed monthly. (3)
- B. Yes, I get my safety labs completed quarterly. (3)
- C. No, I get my safety labs completed less frequently than quarterly. (1)
- D. No, I do not get any lab work completed regularly for my IPF medication. (0)
- E. This is not applicable to me because I am currently not on prescribed IPF medication. (n/a)

Do you wear your oxygen as prescribed?

- A. Yes, I wear my oxygen as prescribed. (3)
- B. No, I wear my oxygen according to how I need it. (1)
- C. No, I do not wear my oxygen. (0)
- D. This question does not apply to me because I am currently not prescribed oxygen. (n/a)

Do you exercise most days a week?

- A. Yes, I exercise every day. (3)
- B. Yes, I exercise most days a week (at least 4 days a week). (2)
- C. No, I exercise less than 4 days a week. (1)
- D. I do not exercise. (0)

Do you take your medication to control reflux / GERD daily?

- A. Yes, I take my medication for reflux / GERD daily and as prescribed. (3)

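### In Appendix 6, daily IPF medication use scores 3 whether or not the patient keeps to the prescription, so the item score cannot tell those two answers apart

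*Combined protocol and SAP*

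**What the plan says.** Appendix 6 (Treatment Compliance Questionnaire, compliance section) opens with this item: "Do you take your IPF medication (nintedanib or pirfenidone) daily and as prescribed". It has five scored options and one for patients to whom it does not apply. Option A, plain daily use, is worth 3 points. Option B reads as follows, its score being the closing figure: "Yes, I take my medication for IPF daily, but not always as prescribed. (3". The other scored options describe less frequent use: C stands for most but not all days and is worth 2, D for fewer than half the days and is worth 1, and E for no use at all and is worth 0. Option F, for patients without a current prescription for an IPF drug, carries no score.

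The introduction to Appendix 6 says that both sections will be scored, that the bracketed values are the compliance key, and how to read the result: "A higher score will reflect an overall greater compliance or knowledge level". The related endpoint is item 2a under Secondary Endpoints: "IPF medication compliance – by patient report/diary". Nothing in the protocol or the statistics section explains why A and B share a value.

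**The concern.** The question joins two conditions, daily use and use in line with the prescription. A patient who meets the first and says that the second is not always met still receives the maximum. The score is meant to rise with compliance, but at the top of this item it does not respond to one of the two things asked about.

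The intervention works on that behaviour. The Visit B management script in Appendix 7 has the nurse ask whether the patient is remembering to follow the prescription, and the management call topics include side effects and dosing. If telenursing changes how closely patients who already take the drug daily keep to the prescription, the item score will not show it. Option A adds to the problem: it mentions daily use only, so a patient who chooses it has not explicitly confirmed the second condition.

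**Working it through.** The plan gives no expected distribution of answers and no target difference for this item, so there is no figure of its own to reproduce. The inputs are the scores in Appendix 6.

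**Step 1. The keys compared.** The third key takes 4/3/2/1/0 and multiplies by 3/4 to return to a 0–3 range.

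| Option | Current | B at 2.5 | 4/3/2/1/0 × 3/4 | B at 2 |
|---|---|---|---|---|
| A | 3 | 3 | 3 | 3 |
| B | 3 | 2.5 | 2.25 | 2 |
| C | 2 | 2 | 1.5 | 2 |
| D | 1 | 1 | 0.75 | 1 |
| E | 0 | 0 | 0 | 0 |

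**Step 2. Moves between options.** If a share f of patients moves from one option to another, the item mean changes by f × (score of new option − score of old option). Under the current key:

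- B to A: f × (3 − 3) = 0 for every f. A to B is also 0.
- C to A: f × (3 − 2) = f.
- C to B: f × (3 − 2) = f, the same credit as C to A.

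With f = 0.40, an assumed value, these are 0, 0.40 and 0.40 points.

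**Step 3. Effect on the arm contrast.** Let d be the share answering B in an interactive arm minus the share in usual care. The current and B = 2.5 keys differ only at B, so

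current contrast − contrast with B at 2.5 = (3 − 2.5) × d = 0.5 × d.

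The documents give no value for d. Over a range of assumed values:

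| d | Difference in contrast (points, 0–3 item) |
|---|---|
| 0 | 0 |
| ±0.30 | ±0.15 |
| ±0.40 | ±0.20 |
| ±1 (arithmetic limit) | ±0.50 |

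**Step 4. Direction.** Start both arms from the same distribution and move f = 0.40 of the interactive arm.

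- B to A (d = −0.40): the current key shows 0.40 × 0 = 0; with B at 2.5 it is 0.40 × 0.5 = 0.20. The current key shows less.
- C to B (d = +0.40): the current key shows 0.40 × 1 = 0.40; with B at 2.5 it is 0.40 × 0.5 = 0.20. The current key shows more.

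The sign therefore depends on which moves occur.

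**Step 5. Other items in the compliance section.**

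- Oxygen: use as prescribed scores 3; use by the patient's own judgement of need scores 1. Departure from the prescription is marked down.
- Reflux medication: the 3-point option names both daily use and the prescription. The item has no option for daily use that departs from the prescription, so it shows only what earns full marks.
- Safety labs: monthly and quarterly both score 3, but that question accepts either interval, so the tie has a basis.

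The medication tie has no such basis, because its question asks for both conditions.

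**The case against.** The best defence is that the key grades frequency. A and B both begin with yes, C to E begin with no, and the scores fall as days of use fall. No less compliant answer outscores a more compliant one, so the tie loses resolution without reversing the order. This stands as a description of the key, but not as a justification: the question asks about the prescription as well, option B exists only to record departure from it, and the oxygen item shows that the instrument does mark such departure down.

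The stakes are also limited. Endpoint 2a is to be measured by patient report or diary, no section names this item's score as the endpoint, and the statistical plan describes an analysis for the primary endpoint only. The item is one of six in the section, so it contributes at most 3 of 6 × 3 = 18 points when all six apply. This stands, and it limits the point to a secondary measure.

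A reader might infer more than the documents support:

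- **That the score cannot separate full from partial adherence.** It separates daily use from most days, fewer than half the days and none. Only the A and B answers are merged.
- **That the endpoint is biased toward no difference.** Step 4 shows that the tie can shrink or enlarge a contrast. If the share answering B is equal in the arms, the contrast is the same under the current key and with B at 2.5.
- **That the education calls teach this behaviour directly.** Education Call 2 is listed as covering drug benefits and risks. The support comes from the management call script.
- **That collected answers can certainly be rescored.** Data Collection lists questionnaire scores and compliance measures; it does not say that item-level answers are kept.

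**Conclusion.** The point holds in a limited form. As written, the key gives full marks to an answer that admits departure from the prescription, on an item that asks about the prescription, and no reason is given. The zero difference between A and B follows from the key and needs no assumption. The sizes in Step 3 depend on the assumed d and on choosing 2.5 as the comparison; for any value b between 2 and 3 given to B, with the other scores unchanged, the difference is (3 − b) × d.

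The consequence is a loss of information, of no fixed direction between arms, in one patient-report measure of secondary endpoint 2a. The primary endpoint is not touched. The point assumes that the item score, rather than the distribution of the lettered answers, will be compared between arms. Appendix 6 suggests this by saying that the section will be scored, but the statistics section does not state it.

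**What to change.** Before any scoring by arm, give B a value strictly between A and C. Two keys do this:

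1. B = 2.5, with A = 3, C = 2, D = 1 and E = 0 unchanged. This alters one number and keeps use on most days at 2, as in the reflux and PAP items.
2. 4/3/2/1/0 rescaled to 0–3. The steps are equal, but C becomes 1.5 and D becomes 0.75, so similar answers would score differently here from those two items.

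Do not set B to 2. That ties B with C, and a move between them would then count as 0.

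For future administrations, extend option A so that it states use in line with the prescription as well as daily use. If the tie is intended, Appendix 6 should give the reason.

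The cost is a small change to the key in Appendix 6 and to the matching scoring in the study database, with no new data. Rescoring answers already collected is possible only if item-level responses were kept, which the sponsor should confirm. The new wording of option A would apply only from its introduction, so that date should be recorded.

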5. To evaluate patient management at ILD Center compared to outlying community centers among the groups and as stratified by class.
6. To evaluate a standardized protocol that includes a structured educational curriculum followed by a regularly timed disease-focused phone calls with protocolized interventions when disease progression is recognized.

Study Design

This is a single-center prospective randomized study to compare outcomes on hospitalization, healthcare compliance, and quality of life of telenursing with or without remote monitoring as compared to usual care. All patients diagnosed with IPF at the Vanderbilt Medical Center outpatient Pulmonary Clinic, who meet inclusion and exclusion criteria, will be asked to participate. Patients who agree to participate and sign consent will be randomized into one of three treatment arms: usual care (the control group), usual care with telenursing, usual care with telenursing and remote monitoring. Patients will be asked to participate in the study for at least one year. We expect to enroll 150 patients, or 50 patients into each arm.

Usual care (Arm 1) – Patients will continue to receive education in the clinic and telephonically about their lung disease, medications, and oxygen use. At the point of diagnosis, patients will be given our current educational materials to take home and review, as well as our contact information. Patients will continue to attend face-to-face visits in the out-patient setting. The frequency of visits will be based on the discretion of the provider. During these visits, the patient will continue to receive individualized standard of care, which may include some or all of the following: a face-to-face visit with a healthcare provider, vital signs, with pulse oximetry at rest, weight measurement, pulmonary function testing, a six-minute walk, and laboratory testing. Other testing, such as echocardiography or chest radiography, may be required based on need. If patients do not return to Vanderbilt Medical Center beyond the point of diagnosis, they will still be allowed to participate. The usual care of local healthcare providers will be collected.

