If patients do not return to Vanderbilt University Medical Center beyond the point of diagnosis, they will still be allowed to participate. Usual care will be completed as described above, with the telenursing arm incorporated. Participants will sign for agreement for their local pulmonary and/or primary care healthcare team to be advised of outcomes of structured telenursing calls.

Usual Care with Telenursing and Remote Monitoring – Patients will continue to receive usual care and telenursing as described above, however, will also be given devices to assist in monitoring objective data points. Patients will receive a hand-held spirometer for home use and a pulse oximeter.

patientMpower. patientMpower is a digital healthcare company providing technology solutions for people with chronic illness who are making strides toward helping patients with idiopathic pulmonary fibrosis. The patientMpower platform is an electronic health journal developed for patients with pulmonary fibrosis to enable them to record objective health data (spirometry, blood pressure, pulse, oxygen saturation and weight), appointments and keep a health journal, medications and obtain reminders to take medications, health surveys, and set exercise goals. The platform is downloaded as an app (free of charge) to the patient’s smartphone or tablet and connected wirelessly to the spirometer and pulse oximeter to allow daily longitudinal monitoring.

After downloading the app, the patient will be able to pair his smartphone or tablet with the spirometer and the pulse oximeter and begin to capture objective data. The mMRC is included within the patientMpower app. Patients will be asked to answer this question as often as they would like, but at least during the telenursing visits. The nursing staff will assist the patient with this process. Recent studies show that pulmonary fibrosis patients are willing and able to use the app to record spirometry and pulse oximetry, as well as symptoms questionnaire (23). More information about the patientMpower app is located in at <https://info.patientmpower.com/ipf/>.

Daily Pulse Oximetry and heartrate. Patients will be given a Nonin 3230 Bluetooth Smart pulse oximeter to measure oxygen saturation at rest on room air or prescribed resting oxygen liter flow. Resting heartrate will be captured simultaneously.

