Purpose 2: IF ASSIGNED TO TELENURSING OR TELENURSING WITH REMOTE MONITORING: the phone call will not only be the usual care appointment follow-up phone call, but will explain telenursing (and remote monitoring, as randomization requires), and set up Educational Phase phone call times, as well as introduce available support groups (local, internet). IF POSSIBLE: The Educational Phone Call # 1 may occur at this time.

Education Phase

Educational phone contact should be scheduled with the patient at his or her convenience and at weekly intervals. The goal is to complete all 8 phone calls within 3 months of enrolling. Please see the power point slide decks associated with each phone call for teaching and script.

Education Phone Call # 1 – review of disease state / procedures / team

Education Phone Call # 2 – IPF FDA-approved medication benefits / risks (or side effects)

Education Phone Call # 3 – tobacco cessation / pulmonary rehabilitation

Education Phone Call # 4 – symptoms management / Importance of wearing your oxygen / AEx

Education Phone Call # 5 – clinical trials

Education Phone Call # 6 – comorbidity management – refer to GI, Sleep, PH (echo)?

Education Phone Call # 7 – lung transplant team (if applicable)

Education Phone Call # 8 – integrative health / palliation / hospice

Management Phase

Management Phone Calls will occur within one week following known provider visits and at intervals between known provider visits to begin within one-week of the post-~3 month follow up visit to discuss outcomes of visit / unanswered or new questions / assurance of follow up. Management Phone Calls will continue until the patient dies or is transplanted. Please see the Management Call power point slide deck or the scripts written below regarding the below topics of discussion:

Med review (side effects, dosing, labs)

Office visits / hospitalization review

Comorbidity review

Assessment of symptoms of AEx IPF / pneumonia / bronchitis /mMRC

PR/Exercise routine?

Oxygen use?

PRN Reminders regarding vaccines

Respiratory Event

If during the process of an educational or management call, the nurses recognizes the symptoms of disease progression or respiratory event, the nurse will utilize the following intervention. Please see the power point slide deck for scripts regarding respiratory event and disease progression.

Associated Script for Telenursing Management Visits

Visit A – within one week of office appointment

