Focus is on ensuring understanding of diagnosis, inform of test results, ensure all orders have been started/completed (medications, referrals, etc), follow-up established.

Greeting

Hello. I'm calling to follow up on your appointment with Dr. ____ / NP ____ this past week at Vanderbilt Medical Center. How are you doing?

General understanding from visit

I just want to follow up to ensure you understand everything about your visit at Vanderbilt. I see from your healthcare provider's note, you were in the office for a ____ visit. Do you have any questions or concerns about your visit?

Review Medical Note – symptom review

During your visit you informed your doctor about your ____ symptoms _____. During the visit, Dr. ____ stated you could do ____ to control these symptoms. How are your symptoms today?

Review Medical Note – procedures / test results

*test results only advised when approved on by the ordering physician.

During your office visit, Dr. ____ ordered some ____ blood tests / xrays / etc. These are / are not back yet. May I review them with you?

Review Medical Note – all follow up

During your office visit, Dr. ____ wanted you to _____. Have these been set up yet?

(referrals for pulmonary rehab, other doctors to evaluate other problems, other studies, medications).

Review of phone call and End of call

Ensure all items have been completed, or are in the works. Ensure understanding of visit / diagnosis. Remind that you will call prior to next appointment.

Visit B – At midpoint between scheduled office appointment

Focus is on health status – is the patient well, or improving, or declining. Also touching compliance regarding medication, oxygen use, and exercise.

Greeting

Hello. This is _____, the _____ at Vanderbilt. I'm calling to check in with you. How are you doing?

Compliance measures

You are taking _____ - are you remembering to take it as prescribed? Any trouble with side effects? How are you managing this? Your pharmacy is _____. Any problems with getting your medications?

Double check lab schedule – have they had labs / need labs?

You are wearing oxygen? Current liter flow is __ with rest and __ with exercise. Your current DME is _____. Any changes to this? Do you have enough oxygen for your needs both inside and outside of your home?

You are exercising? Pulmonary Rehabilitation or at home? How many days a week?

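### The plan states no common source or schedule for finding hospitalizations, and the only hospitalization review it describes goes to Arms 2 and 3

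*Combined protocol and SAP*

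**What the plan says.** **Endpoint.** The analysis plan for the primary endpoint (Statistics) defines an ordinal variable over one year from diagnosis. Its categories are the number of hospitalizations among patients who are alive, with death as the worst. The Endpoints section speaks of hospitalizations for respiratory events.

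**Hospitalization review.** Appendix 7, Management Phase, lists "Office visits / hospitalization review" among the topics of the Management calls. Their timing is: "Management Phone Calls will occur within one week following known provider visits and at intervals between known provider visits". They start after the follow-up visit at about three months, and "Management Phone Calls will continue until the patient dies or is transplanted". They belong to telenursing, so Arm 1 does not receive them.

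**Care away from the centre.** Under Study Design, "The frequency of visits will be based on the discretion of the provider". For the telenursing arm: "If patients do not return to Vanderbilt University Medical Center beyond the point of diagnosis, they will still be allowed to participate". Arm 1 has the same rule, followed by: "The usual care of local healthcare providers will be collected". No method is given.

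**Data items.** Data Collection lists admission and discharge dates, admitting diagnosis and cost of hospitalizations. It does not restrict these to any arm, and it names no source and no schedule.

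**Questionnaires.** All arms complete questionnaires at diagnosis, month 3, month 6 and every six months after that. The printed forms (mMRC, depression, anxiety, and compliance and knowledge; Appendices 3 to 6) contain no question about admissions. The SGRQ-I, the L-IPF, the telenursing slide decks and the study flowchart are not reproduced and cannot be checked.

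**The concern.** An endpoint that counts admissions depends on someone learning of each one. The centre can see its own admissions, but some patients will be followed, and so probably admitted, elsewhere. For those patients the only hospitalization review described is in calls that randomization gives to two arms and withholds from the third.

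If Arm 1 admissions are found less completely, Arm 1 looks healthier than it is and the benefit of telenursing is understated. More patients would not reduce such a bias. The planned analysis would not detect it either, because an admission that nobody learns of is not recorded as missing. Secondary endpoint 4 (time to first hospitalization, number per patient, length of stay) would rest on the same records.

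**Working it through.** The documents give no capture rate and no number of hospitalization reviews, so there is no figure to reproduce. The check sets the described routes side by side and then follows an unfound admission through the endpoint.

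**Step 1. Routes by which the study could learn of an admission**

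| Route | Arm 1 | Arms 2 and 3 | Source or schedule for admissions stated? |
|---|---|---|---|
| Clinic visits (Study Design) | Yes | Yes | No; frequency is left to the provider |
| Usual-care telephone contact (Study Design, Appendix 7) | Yes | Yes | No |
| Collection of local usual care (Study Design) | Stated | Usual care as in Arm 1 | No method or timing |
| Hospitalization fields (Data Collection) | Listed | Listed | No |
| Readable all-arm questionnaires (Appendices 3 to 6) | No item | No item | Not applicable |
| Educational calls (Appendix 7) | No | 8 calls | No hospitalization topic listed |
| Management calls (Appendix 7) | No | Yes | Listed topic; timing follows known provider visits |

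The last two rows differ by arm, and only the last names hospitalizations as something to review.

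**Step 2. Effect of an unfound admission on the score**

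- Alive at one year, one admission, not found: scored in the best category.
- Alive, two admissions, one not found: scored one category too low.
- Dead within the year: scored as death whether or not the admission was found, assuming deaths are found equally in all arms.

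So only patients who survive the year can be misplaced in the primary endpoint. The sensitivity analysis of hospitalization rates without death lacks even that protection, and it uses the same records. Multiple imputation is planned for missing data, but an unfound admission leaves no gap to impute.

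**Step 3. What the size would depend on**

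Let *r* be the true Arm 1 risk of hospitalization, *s* the share of those patients alive at one year, and *u* the shortfall in capture among them relative to Arms 2 and 3. The Arm 1 proportion placed correctly outside the best category is then *r*(1 − *us*).

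The protocol's largest scenario has *r* = 0.25, Arm 2 at 0.25 × 0.77 = 0.1925 and Arm 3 at 0.25 × 0.58 = 0.145. The values of *u* and *s* below are assumptions; the documents give neither.

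- *u* = 0: Arm 1 stays at 0.25. The differences are 5.75 points (Arm 2) and 10.5 points (Arm 3), and nothing is lost.
- *u* = 0.10, *s* = 1: 0.25 × 0.90 = 0.225. The differences are 3.25 and 8.0 points.
- *u* = 0.10, *s* = 0.5: 0.25 × 0.95 = 0.2375. The differences are 4.5 and 9.25 points.

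These lines show the direction and how strongly the result depends on *u* and *s*. They use a binary summary like that of the protocol's simulation, not the ordinal endpoint, and are not an estimate of the bias.

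**The case against.** The strongest reply is that nothing shows the calls to be the data source. Data Collection lists hospitalizations separately from the outcomes of telenursing calls, for all patients. Admitting diagnosis and cost point to records rather than recall, and medical record number and dates of service are also collected. Every patient must accept notification of local practices. Arm 1 keeps clinic visits and telephone education, so admissions may surface there too. The sponsor may well intend one records search for everyone.

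Most of this stands. Unequal capture is a possibility left open by silence, not something the documents show. What remains is that no common procedure is written, and notifying a local practice is not the same as retrieving its hospital records.

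Three stronger readings are tempting and are not supported:

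- **Six reviews against none.** With visits every three months, calls after months 3, 6 and 9 and at months 4.5, 7.5 and 10.5 make six. But visit spacing is not fixed (six-monthly visits would give three or four). The review is one line in a topic list, and the printed Visit A and Visit B scripts contain no hospitalization question. Nor does the absence of a described review in Arm 1 mean absence of contact.
- **A definite loss of effect.** The capture shortfalls are assumed. Within Arms 2 and 3, patients with few known visits may themselves be asked less often, which works the other way. The net result cannot be computed.
- **A defect that needs a fixed call interval.** How often to call a patient with no known visit is a question of intervention dose. Known visits are not limited to the centre, so such patients may be rare. Once admissions are found the same way in all arms, call timing no longer drives the primary count.

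**Conclusion.** The concern holds as a gap in how the primary endpoint is ascertained. The one hospitalization review described goes to two of three arms, while the data items that apply to all arms have no stated source or schedule. The plan as written therefore allows capture to depend on contact, and contact depends on assignment.

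The likely direction is against telenursing. The size is unknown and is zero if capture is equal. In the primary endpoint it is limited to patients who survive the year. This rests on two assumptions: that some admissions occur outside the centre's own records, and that deaths are found equally in all arms. Material not reproduced, such as the slide decks or the two quality-of-life instruments, could narrow the gap.

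**What to change.** 1. Ask all three arms the same short hospitalization questions (any admission since the last form, dates, hospital, reason) with the questionnaires already due at months 3, 6 and 12. The reason is needed because the Endpoints section counts respiratory events.
2. Confirm each reported admission from the discharge record. Apply any wider records search in the same way and on the same dates in each arm.
3. Build the primary count from these common sources and record the source of each admission. Add admissions learned only from telenursing calls in a sensitivity analysis.

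**Cost.** Entries: 150 patients × 3 forms = 450, with no new contacts. Patients needing discharge records: 50 × (0.25 + 0.19 + 0.15) = 29.5 under the protocol's largest effect, or 150 × 0.25 = 37.5 with no effect, so roughly 30 to 38, some with more than one admission. The larger burden is the uniform record check, which covers all 150 patients and may involve outside hospitals. The Management call schedule can stay as it is.
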